competing abroad, sleep schedules and circadian rhythms may be out of control. Prior to major competitions, 64% of athletes report partial sleep deprivation (5). It can be reasonably deduced that partial sleep deprivation may have an impact on physiological rhythms, which in turn may affect athletic performance.

Caffeine is a beneficial nutrient that has been demonstrated to enhance athletic performance (6). It has been demonstrated that caffeine supplementation prior to exercise has a significant impact on improving endurance performance and reducing fatigue index in athletes. In sports requiring explosive power or agility, the effect size of caffeine was observed to be approximately small to moderate (7). In order to achieve a significant boost in pre-workout strength and explosiveness in explosive sports, a higher dosage of caffeine is required (8). However, supplementation with higher doses of caffeine may cause insomnia or affect sleep quality (9). One potential method for addressing insomnia may be to utilize smaller doses of caffeine prior to exercise, while still achieving a beneficial stimulant effect.

Caffeine gum can be absorbed through the mucous membranes of the mouth, resulting in a faster absorption rate of caffeine (10), which may also have a higher effect size on athletic performance (11). Based on past literature, chewing smaller doses of caffeinate chewing gum has been found to improve lower body strength and explosive performance (12). It may be posited that the use of chewing gum as a caffeine supplement could prove an effective method of enhancing athletic performance without adversely affecting sleep quality. Caffeine supplementation can be effective in improving explosive power and vertical jump height during fatigue after partial sleep deprivation (9). However, there are no published studies investigating the impact of partial sleep deprivation on the physical performance of ice hockey players, whether on-ice or off-ice. The purpose of this study was to examine the impact of ingesting caffeinate chewing gum on the on-ice and off-ice athletic performance of hockey players experiencing partial sleep deprivation.

Methods

Experimental Design

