This study used a randomisation crossover design with a single-blind, double-blind experimental design. The participants were randomly assigned to either a caffeinated chewing gum trial (CAF) or a placebo trial (PL). After the first main trial, participants rested and recovered for 7-10 days before proceeding to the next trial. All participants completed all tests within one month. During the study period, all participants

maintained their normal training status, with no changes in the training program, and no over-training or extra competitions. This is the out-of-season training period for players.

Participants

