Fourteen trained ice hockey players (Age: 25.2 ± 5.4 ; height: 176.5 ± 5.3 ; weight: 78.1 ± 13.4) were recruited to participate in this study, including six defensemen, two centres, and six forwards. All participants had more than 6 years of professional hockey training and were familiar with all hockey skills. Inclusion criteria: 1. 6 years of professional ice hockey training, 2. 6 months of continuous training, 3. 3 months of recovery from sports injuries such as strains and sprains. Exclusion criteria: 1. non-specialised ice hockey player. 2. has not trained regularly for the past 6 months. 3. has recovered from an athletic injury. 4. have been recovering from a sports injury for less than 3 months, or have epilepsy, hypertension, hyperlipidemia, heart disease, arthritis, osteoporosis, brain injury, or a history of caffeine allergy. In a past study, the effect of caffeinated chewing gum was found to have an effect size (Cohen's d) = 1.00 on the fatigue index of basketball players (11). The G*POWER statistical software (latest ver. 3.1.9.7; Heinrich-Heine-Universität Düsseldorf, Düsseldorf, Germany) indicated that eight participants were sufficient to interpret the data for the purposes of the study, with a power value of 0.8. In order to achieve a more precise POWER value, the number of participants in this study was set to 14. All participants provided written informed consent after being fully informed about the potential risks involved in the experiment, in accordance with the ethical standards of the relevant academic institution. A signed consent form was obtained from each participant. The order of participants was determined through the use of computerized randomization software (Excel Office 365). This study received approval from the Institutional Review Board of Jen-Ai Hospital - Dali Branch (202300071B0). All the data were performed at the indoor stadium. This study was conducted following the Declaration of Helsinki.

Protocol

All participants were required to perform the exercise-specific tests at least 2 times prior to the formal trial to familiarise themselves with the process of the formal trial. Participants were asked to record their diet 3 days before the first formal trial and were asked to repeat the same diet before the next trial. The following experiments were scheduled to start at 11 p.m. Upon arrival at the designated Ice hockey arena, the participants were granted a 10-minute rest.

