The caffeinated chewing gum used in this study, specifically Military Energy Gum (Arctic Mint flavor; Stay Alert, Chicago, USA), has been previously utilized in other studies (12, 17). Each piece contained 100 mg of caffeine, with a 5 g gum base. The gum was provided in various weights, according to the relative dosage. A commercially available blue mint gum was used as the placebo. To achieve a target dose of 3 mg caffeine per kilogram of body weight and maintain a double-blind design, all chewing gums were mashed, ground, homogenised, and reshaped after incorporating 0.3 g of peppermint flavouring powder. This ensured that the colour, appearance, taste, weight, and size of the gum types were indistinguishable. All chewing gums were prepared by

specialized individual and given to the on-site testers after numbering.

Statistical Analysis

All data are presented as means \pm standard deviations. The normality of the data distribution was assessed using the Shapiro–Wilk test. The grip force, CMJ, SJ, 35 metre sprint, S-Shape agility test and Yo-Yo intermittent recovery test were employed to analyses the through paired t-tests. The magnitude of the observed effects was quantified using Cohen's d, a measure of effect size. The power value of each data was conducted using G*Power 3.1.9.6 software (18). All data were calculated using SPSS (version 20, Chicago, IL, USA), and the significance level was $p < 0.05$.

Reference

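### Paired t-tests leave visit order out of a two-period crossover: a prespecified period term is a cheap safeguard, with a gain that depends on an undocumented visit difference

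*Protocol*

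**What the plan says.** Experimental Design sets out two trials per player in randomised order: "After the first main trial, participants rested and recovered for 7-10 days before proceeding to the next trial". On generating that order, Participants says "The order of participants was determined through the use of computerized randomization software (Excel Office 365". It gives no number per sequence and no blocking or balancing rule.

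Statistical Analysis states that grip force, the two jumps, the 35 m sprint, the S-shape agility test and the Yo-Yo test "were employed to analyses the through paired t-tests". Visit and sequence are not mentioned.

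Three provisions limit a difference between visits:
- Protocol section, familiarisation: "All participants were required to perform the exercise-specific tests at least 2 times prior to the formal trial".
- Protocol section, diet: players "were asked to repeat the same diet before the next trial".
- Experimental Design, training: players "maintained their normal training status, with no changes in the training program, and no over-training or extra competitions".

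The sample-size paragraph in Participants takes a Cohen's d of "1.00 on the fatigue index of basketball players (11", finds eight players sufficient for power 0.8, and sets the number at 14.

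**The concern.** Half the point of randomising order is that a change from visit 1 to visit 2 (practice, motivation, ice conditions) can be separated from the treatment effect. A paired t-test of CAF minus PL does not separate them. With unequal sequences, part of any such change is counted as a caffeine effect or hides one. With equal sequences it cancels from the mean but stays in the SD of the differences, so the test becomes conservative.

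The protocol itself fixes the paired t-test, so this is a stated choice and not a detail left to an unseen SAP. At stake are some power and interval width, and a possible shift in the estimate at the one split that was actually realised.

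**Working it through.** **Inputs from the protocol.** n = 14; two visits; d = 1.00; significance level 0.05.

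**Assumptions.** d is the effect in SDs of the within-player difference; tests are two-sided (sidedness is not stated); the visit difference π (visit 2 minus visit 1, same SD units) ranges over 0, 0.25, 0.5 and 1.0. No value of π is in the documents.

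**The protocol's own figure.** By the noncentral t distribution at d = 1.00, n = 8 gives power 0.815 one-sided and 0.681 two-sided; two-sided, n = 10 gives 0.803. The stated 8 is thus reproduced one-sided. For n = 14, two-sided, power is 0.932, which is the baseline below.

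**Model.** Let τ be the treatment effect, n1 the players with PL first and n2 those with CAF first. The CAF − PL difference has mean τ + π for PL first and τ − π for CAF first, with SD 1.
- Paired estimate: mean τ + π(n1 − n2)/14, variance 1/14.
- Expected sample variance of the differences: 1 + 4π²n1n2/(14 × 13).
- Period-adjusted estimate: mean τ for any π, SE = 0.5√(1/n1 + 1/n2), 12 df.

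**Equal sequences (7:7).** Bias is 0. At π = 0.5 the expected variance is 1 + 4 × 0.25 × 49/182 = 1.27, so the SD is about 1.13. Power at d = 1.00:

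| π (SD) | Paired | Adjusted |
|---|---|---|
| 0 | 0.932 | 0.929 |
| 0.25 | 0.923 | 0.929 |
| 0.5 | 0.890 | 0.929 |
| 1.0 | 0.725 | 0.929 |

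The two are equal at π of about 0.15. With τ = 0 and π = 0.5 the paired test rejects in about 3% of trials, so it is conservative.

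**Unequal sequences, π = 0.5.** The shift at 8:6 is 2/14 × 0.5 = 0.07; at 9:5, 4/14 × 0.5 = 0.14; at 10:4, 6/14 × 0.5 = 0.21. Paired power depends on the direction of the visit effect:

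| Split | Shift (SD) | Paired power, d = 1.00 | Adjusted power | Paired type I error |
|---|---|---|---|---|
| 8:6 | 0.07 | 0.93 or 0.84 | 0.92 | 0.03 |
| 9:5 | 0.14 | 0.96 or 0.78 | 0.91 | 0.05 |
| 10:4 | 0.21 | 0.98 or 0.71 | 0.87 | 0.08 |

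At π = 0.25 the shifts are half as large: 0.04, 0.07 and 0.11.

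**Average over simple randomisation (assumed, not stated).** The shift averages to zero because n1 − n2 has mean zero. Type I error is 0.050 to 0.051 over this range of π. A split of 10:4 or worse has probability 0.18. Average power at d = 1.00 is 0.93, 0.92, 0.87 and 0.68 paired at π = 0, 0.25, 0.5 and 1.0, against 0.91 adjusted; they are equal at π of about 0.34.

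**Bias against precision.** Setting 1/14 + π²(n1 − n2)²/196 equal to 3.5/(n1n2) gives π = √(3.5/(n1n2)): 0.27 at 8:6, 0.28 at 9:5 and 0.30 at 10:4. Below these values the paired estimate has the smaller mean squared error despite its bias.

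**The case against.** The paired t-test is a common and valid analysis of this design, and nothing in the protocol shows either a remaining visit difference or an unequal split. Familiarisation, diet and training control make a large difference less likely. At 0.25 SD the harm is slight: power 0.932 to 0.923 at 7:7, or a shift of 0.04 SD at 8:6. Adjustment also loses precision exactly where the bias argument applies, at unequal splits. All of this stands, and it is why the point is no more than an optional improvement. It does not remove the point: the three provisions limit a visit difference without excluding one, and the estimate will be read at the realised split, not averaged over splits.

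A reader might infer more, without support in the documents:
- That the planned test is invalid or the caffeine estimate is biased. Over simple-randomisation splits it is neither, and at 7:7 there is no bias at all.
- That the sequences were unbalanced. The protocol is silent on this, and silence is not evidence of imbalance.
- That the protocol expects smaller effects for most of its outcomes, so that the loss is relatively larger. The Introduction says "In sports requiring explosive power or agility, the effect size of caffeine was observed to be approximately small to moderate (7", but that reports findings for caffeine in general, and its next paragraph adds that gum may have a larger effect. At an assumed d = 0.5, 7:7 and a 0.5 SD visit difference, power is 0.32 paired and 0.41 adjusted; that scenario is this review's assumption, and power is low with either test.

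**Conclusion.** The point holds as a cheap, conditional improvement. The planned analysis ignores visit order and the sequence balance is not stated, but the test remains valid. The gain from a period term rests on a visit difference whose size the documents do not give. At 7:7 and d = 1.00, adjustment recovers about 4 percentage points of power at an assumed 0.5 SD (0.89 to 0.93) and about 1 point or less at 0.25 SD. At unequal splits it removes a shift of 0.07 to 0.21 SD (8:6 to 10:4, at 0.5 SD), at some cost in precision. The case is clearest if the randomisation list was balanced. If it was simple, adjustment raises average power only above about 0.34 SD. All figures assume a two-sided 5% test and d in SDs of the within-player difference.

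**What to change.** For each outcome, prespecify a model with treatment and period as fixed effects and player as random effect. Fix this in advance, without first testing for a period effect. Report the treatment difference with its 95% CI and, as a reporting item, the number of players in each sequence.

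With complete data, a two-sample t-test comparing within-player period differences (visit 2 minus visit 1) between the sequences gives the same p-value. Its group means are π + τ and π − τ, so it estimates 2τ: the mean difference and both CI limits must be halved to give the treatment effect.

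If outcome data have already been seen, date the change and show the paired t-test beside it. The protocol already reports sleep and waking hours by condition; that alone does not show that outcomes were known.

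Cost: one line of analysis wording and no new data. At 7:7 with no visit difference, one degree of freedom is lost (power 0.932 to 0.929). At 8:6, 9:5 and 10:4, adjusted power is 0.92, 0.91 and 0.87, against 0.93 for the paired test when there is no visit difference.
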